2.2.4 Correlative Studies Background

With more effective chemotherapy and radiation treatment delivery it is increasingly important to identify molecular subtypes that may require dose escalated or targeted therapy. The traditional Lauren classification²⁶ and World Health Organization²⁷ systems categorize gastric tumors by histology and have had limited utility in guiding oncologic therapies or targeted drug discovery. Currently, the only clinically meaningful molecular biomarker is Her2/neu overexpression, with the TOGA trial demonstrating an OS advantage in Her2/neu positive gastric cancer patients treated with trastuzumab plus chemotherapy versus chemotherapy alone²⁸. Unfortunately, only 6-20% of gastric adenocarcinomas demonstrate Her2 overexpression and/or amplification²⁹. Other attempts to classify gastric tumors via microarray and whole transcriptome sequencing were limited by small sample sizes, no associated clinical outcomes, and the use of immortalized cell lines instead of original patient pathology^{30–33}. In contrast to the parallel technologies that guide the management of breast^{34,35} or prostate cancer^{36,37}, there are no clinically implemented biomarker panels or strata that predict or prognosticate outcomes for gastric cancer.

TCGA performed a multiple platform analysis of 295 treatment naïve gastric cancer samples using array-based somatic copy number analysis, whole-exome sequencing, array-based DNA methylation profiling, messenger RNA sequencing,

microRNA sequencing and reverse-phase protein array. They proposed a four molecular subgroup classification system (Figure 1)³⁸. However, the study was performed on treatment naïve tissue, with the potential for high molecular heterogeneity inherent to gastric cancer³⁹. Due to the sample size that was likely restricted by the high cost of multiple platform genomic analysis, it is possible that the heterogeneous cellular makeup of the gastric tumors deterred the detection of consistently differentially expressed biomarkers in the study. Data in esophageal adenocarcinoma indicate that

[figure not shown]

Figure 1. TCGA molecular subtypes of gastric adenocarcinoma. EBV, Epstein-Barr virus; MSI, microsatellite instability; SCNA, somatic copy-number aberrations.

chemotherapy reduces tumor heterogeneity (Figure 2)⁴⁰ and post-chemotherapy cell populations may preferentially express genes that promote survival⁴¹. Evaluating biomarkers in a more molecularly uniform cell population may increase the ability to detect clinically significant molecular subgroups.

[figure not shown]

Figure 2.DNA copy number as surrogates for tumor variation; decreased heterogeneity in the chemotherapy plus surgery (CS) vs surgery alone (S).

growing data There are implicating the role of microRNAs (miRs), small noncoding RNAs that regulate mRNA expression, in regulating response to chemotherapy and ionizing radiation⁴⁹. Researchers have demonstrated that increased miR-21 and miR-106a may target phosphatase and tensin homolog (PTEN), resulting in gastric cancer resistance to

cisplatin chemotherapy^{50,51}. While miR data regarding radiation therapy are limited in gastric cancer due to only sporadic use of preoperative radiation, there are data indicating increased miR-31 levels confer radiation sensitization in esophageal adenocarcinoma⁵³. The expression levels of these miRs after preoperative chemoradiation therapy in addition to their prognostic and therapeutic implications in gastric adenocarcinoma are not known.

Cell-free DNA is a powerful non-invasive assay for quantitating tumor disease burden^{54,55}. Circulating tumor DNA (ctDNA), the tumor component of cell-free DNA, is indicative of molecular residual disease in colorectal cancer patients and

has prognostic value^{56,57}. Other investigators have shown similar findings in breast ⁵⁸, lung⁵⁹, cervical⁶⁰, and pancreatic cancer⁶¹. There are limited data on ctDNA in gastric cancer⁶².

2.3 Study Design

2.3.1 Overall Design

The hypothesis of this study is that adaptive SCRT followed by multiagent chemotherapy will result in a pCR of at least 20%.

Thirty-six patients with gastric adenocarcinoma will be enrolled in this study. There will be a lead-in cohort of 5-10 patients (see Safety Cohort and Early Stopping Rules) to ensure there are no grade 5 toxicities related to adaptive SCRT (or SOC chemotherapy after adaptive SCRT). All patients will receive radiation delivered with MR or CBCT guidance followed by sequential chemotherapy. Gastrectomy will occur 2-4 weeks after the completion of chemotherapy. Pathologic response, plan dosimetry, and oncologic outcomes will be evaluated. FDG PET/CTs are strongly encouraged at baseline but optional. Patients will be followed on study for 12 months after surgery.

2.3.2 Scientific Rationale for Study Design

This study will be a non-randomized, single arm, phase II study with all patients receiving preoperative radiation therapy then SOC chemotherapy followed by surgical resection. The reason for performing a non-randomized trial is to evaluate the clinical efficacy of this treatment regimen in a timely manner. Due to the infrequent incidence of this disease in the United States (Washington University in St. Louis performs approximately 30-50 gastrectomies per year for gastric cancer), a randomized control trial would take many years to complete. We will compare the dosimetric and clinical outcomes to historical controls.

2.3.3 Justification for Dose

Twenty-five Gy in 5 fractions is a dose fractionation used for aggressive palliation of intraabdominal malignancies. It is well tolerated and usually prescribed without dose constraints (if delivered with at least four fields). This dose and fractionation to the whole pelvis is a standard of care treatment regimen in patients with rectal adenocarcinoma. This is also the dose and fractionation that is prescribed to the whole pelvis for non-operative management of rectal adenocarcinoma at our institution. at the time of this protocol submission, this short course radiation therapy followed by 4 months of chemotherapy leads to greater than 70% cCR of rectal adenocarcinoma in our institutional experience and prospective phase I trial (NORMAL-R, HRPO# 201512140). We anticipate it will be well tolerated in gastric adenocarcinoma patients with high clinical response when coupled with multi-agent chemotherapy.

3.0 OBJECTIVES AND ENDPOINTS

Objectives	Endpoints	Justification for Endpoints
Primary		•
To quantify the pCR rate in gastric cancer patients treated with preoperative radiation	The rate of pCR (both ypT and ypN) in gastric cancer patients treated with	A complete pathologic response may result in improved oncologic
followed by total neoadjuvant chemotherapy.	preoperative radiation followed by total neoadjuvant chemotherapy.	outcomes. High rates of pCR may lead the way for future studies of non- operative management of gastric cancer.
Secondary		
To quantify the proportion of patients able to complete a full course of total neoadjuvant chemotherapy	Proportion of patients able to complete a full course of total neoadjuvant chemotherapy.	Evaluating the feasibility of total neoadjuvant therapy will help guide future trials seeking to maximize response prior to surgery.
To quantify the local control rate of gastric cancer patients treated with preoperative radiation followed by chemotherapy.	The local control rate at 1 year post RT.	Providing radiation therapy prior to chemotherapy and surgery may increase the local control rate.
To quantify the toxicity of gastric patients treated with preoperative radiation followed by chemotherapy.	The rate of grade 3 or greater toxicity as defined by CTCAE v 5.0.	Adding radiation therapy to chemotherapy and surgery may increase the toxicity associated with treatment.
To quantify the overall survival in gastric cancer patients treated with preoperative radiation followed by chemotherapy.	The overall survival at 1 year post RT.	By improving local control and pCR, overall survival may be improved.
To quantify the disease free survival in gastric cancer patients treated with preoperative radiation followed by chemotherapy.	The disease-free survival at 1 year post RT.	By improving the local control, disease free survival (locoregional and distant recurrence) may be improved as well.
Tertiary/Exploratory		
To quantify the deviation in dose to the tumor due to variation in stomach position.	Average percent difference in coverage of PTV by 95% isodose line.	The average percent difference of the five treatments represents approximately what percent of the total planned prescription was delivered to the target. Under-dosing of the tumor due to organ

[motion may regult in
		motion may result in
		decreased tumor control.
To quantify the deviation in dose	Average percentage	The average percent
to OARs due to variation in	difference in dose to nearby	difference of the five
OAR position.	OARs (i.e. duodenum, small	treatments represents
	bowel, large bowel) due to	approximately what percent
	variation in OAR position.	of the total planned
		prescription was delivered
		to the OAR. Over-dosing of
		the OARs due to organ
		motion may result in
		increased toxicity.
To determine the distribution of	The percentage of patients in	Treatment with radiation
TCGA molecular subtypes in	each TCGA molecular	and chemotherapy may
gastric adenocarcinoma after	subtype after radiation and	select for a different
radiation and chemotherapy.	chemotherapy.	distribution of TCGA
		molecular subtypes.
To identify differentially	The specific biomarkers	Treatment with radiation
expressed post-treatment	-	and chemotherapy may
biomarkers		select for a less
		heterogeneous, clinically
		significant biomarker
		enriched tumor subtype.
To correlate circulating tumor	ctDNA levels	ctDNA may detect
DNA (ctDNA) levels with		treatment refractory disease
clinical outcomes.		and residual tumor earlier
		than traditional modalities.

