2.2.3 Adaptive Radiation Therapy

The ViewRay system is a MRgRT coupled LINAC machine (ViewRay Inc., Oakwood Village, OH). The 0.35 Tesla real-time MR imaging allows radiation to be delivered to the tumor only when the target is in the designated treatment area. Traditional 3D CT planned radiation contours include a margin to account for respiratory motion, internal organ motion and setup error. MRgRT may permit smaller margins resulting in lower dose to normal structures²³. Daily plan adaptation is possible with physicians contouring OARs, and subsequent changes in beam arrangements or dose to meet dosimetric constraints. Not only can this imaging guided treatment ensure prescribed dose delivery, it may permit dose escalation or boost volumes for gross tumor²³. To date there is no clinical trial that has prospectively evaluated the feasibility or oncologic outcomes of preoperative MRgRT plus concurrent chemotherapy in gastric cancer.

At Washington University, we treat pancreas, liver, breast and other intraabdominal and thoracic tumors with MRgRT. Our preliminary data for stomach motion during definitive (non-operative) radiation treatment of gastric lymphoma (Figure 1) indicate that even with patient instructions for NPO 3 hours prior to treatment, the daily stomach position can vary up to 2.95 cm from the planning position. Motion assessment of 5 patients with gastric lymphoma show a mean translational distance (calculated from x, y and z displacement) of 1.3 ± 0.5 cm. The patients' average stomach volume was 763 cc, with 29.5 ± 19.0 cc outside the 5 mm PTV margin due to daily changes in stomach position over 20 fractions.

To date we have treated four patients with gastric adenocarcinoma with MRgRT 25 Gy in 5 fractions. The patients were treated with this fractionation to palliate symptoms or due to medical inoperability. Patients tolerated the treatment without treatment related acute grade 3+ toxicity. One patient that subsequently underwent sequential chemotherapy and surgical resection was not noted to have increased fibrosis or issues with resectability.

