6.2 Radiation Therapy Guidelines

6.2.1 Dose, Fractionation, and Constraints

When feasible it is strongly recommended that radiotherapy begin on a Monday. It is accepted that occasional logistical delays may occur during radiotherapy treatment due to machine downtime or other issues. Radiotherapy as administered during this study may take up to 10 business days without being considered a protocol deviation.

Radiotherapy will consist of five fractions, delivered once daily, to a total dose of 25 Gy at 5 Gy per fraction. Radiation must be delivered with daily adaptive planning and MR gating or CBCT breath hold treatment. The stomach and OARs must be redrawn each day for the adaptive plan. Plans should be adapted to meet OAR constraints or improve coverage as needed for each day's unique anatomy.

Coverage: PTV V95% = 100%

Luminal GI structures: 30 Gy < 0.5 cc (hard constraint). 25 Gy < 0.5 cc (soft constraint). Kidneys V18 < 200cc. Spinal cord V28 < 0.03cc.

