6.2.4 Clinical Target Volume (CTV) and Planning Target Volume (PTV) Definitions

The CTV_primary will include the stomach GTV (as per PET/CT and endoscopy report) plus a 1-3 cm proximal-distal expansion along the length of the bowel structure (i.e. stomach, esophagus, or duodenum as applicable) This range is provided to allow more coverage near the GE junction (akin to esophageal expansions) but to prevent irradiating the entire stomach. Expansion may extend into esophagus and/or duodenum per tumor location. A 1-1.5 cm radial expansion is generated for CTV primary, cropped to GI luminal structure. Clinically suspicious locoregional lymph nodes as identified by EUS or imaging that are visible on 0.35 T MR may be included with a 1.0 cm expansion to CTV_node (or included in CTV_elective)). Both the CTV_primary and CTV_node must be evaluated for change and re-contoured daily at the machine if significantly changed per reviewing MD assessment. If the LN is not visible then the gross node CTV volume should not be changed.

CTV is generated with a 1-1.5 cm brush, creating a semicircle volume encompassing the proximal 1-1.5 cm of celiac SMA vessel, with the aorta at its posterior border and the anterior border demarcated by bowel or pancreas. Ideally, CTV_elective should not change if treatment imaging is acquired in the same position and phase of breathing as the simulation scan.

PTV is generated by a uniform 1 cm expansion about the CTV. Reducing PTV margins to modify OAR dose(s) is not permitted.

For daily adaptive treatments, patient should be aligned to CTV_elective. GTV is rigidly deformed and redrawn to match daily anatomy of stomach using diagnostic

imaging and prior fraction treatment plan. CTV_primary is created as above.

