6.2.6 Retrospective Plan Review

Deidentified DICOM datasets will be sent through encrypted transfer to Washington University for central review of contours and treatment plans. Initial radiation treatment plans will be overlaid on each daily anatomy and the change in dose to PTV and OARs will be determined.

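### Exploratory endpoint 1 reads PTV coverage as dose to the tumor, so the planned interpretation overstates tumor under-dosing from stomach motion

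*Combined protocol and SAP*

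**What the plan says.** The objective in section 3.0 is "To quantify the deviation in dose to the tumor due to variation in stomach position". Its endpoint is "Average percent difference in coverage of PTV by 95% isodose line". The justification column states that "The average percent difference of the five treatments represents approximately what percent of the total planned prescription was delivered to the target", and goes on to say that under-dosing of the tumor from organ motion may reduce tumor control.

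Section 6.2.4 defines the measured volume: "PTV is generated by a uniform 1 cm expansion about the CTV". Section 6.2.1 requires the 95% isodose to cover the whole PTV at planning. Section 2.2.3 explains what margins are for: "Traditional 3D CT planned radiation contours include a margin to account for respiratory motion, internal organ motion and setup error".

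The data come from the central review in section 6.2.6: "Initial radiation treatment plans will be overlaid on each daily anatomy and the change in dose to PTV and OARs will be determined". Section 6.2.4 has the GTV redrawn and CTV_primary rebuilt from it for each adaptive fraction, and section 6.2.2 makes dose-volume histograms for the target volumes mandatory. Even so, no endpoint is defined on the GTV or CTV.

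**The concern.** The quantity named in the objective (tumor dose) and the quantity measured (PTV coverage) respond differently to motion. The overlay keeps the dose fixed where it was planned and moves the anatomy. The daily PTV is grown afresh around the moved CTV, so its leading edge leaves the planned dose as soon as anything moves. The CTV does not leave it until the 1 cm margin is used up. PTV coverage therefore records loss of safety margin first and loss of target dose only later.

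The justification in section 3.0 has two further problems. V95% is the fraction of a volume that receives at least 95% of the prescription; it is not a percent of the prescription. And the overlay applies the initial plan without adaptation, so it does not describe what was delivered to a patient who was treated with daily adapted plans.

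At stake is how the dosimetric result will be read. A report that follows section 3.0 would describe tumor under-dosing on days when the contoured target lay wholly inside the planned isodose. This is also the only planned endpoint on how motion affects target dose.

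**Working it through.** **Inputs from the documents.** PTV margin 1 cm (6.2.4). Planned PTV V95% of 100% (6.2.1). From section 2.2.3, in 5 gastric lymphoma patients: mean displacement 1.3 ± 0.5 cm, maximum 2.95 cm, mean stomach volume 763 cc, and 29.5 ± 19.0 cc outside a 5 mm margin. The documents give no figure for the gap between PTV and CTV loss, so there is none to reproduce.

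**Assumptions.** The CTV is a sphere of radius r (3, 4 or 5 cm, or 5.67 cm, which corresponds to 763 cc). The target shifts rigidly by d. The 95% isodose ends exactly at the planned PTV edge, R = r + 1. The daily PTV is the CTV after the shift plus 1 cm.

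**Formulas.**
- PTV loss (two equal spheres of radius R): 3d/(4R) − d³/(16R³).
- CTV loss: zero if d ≤ 1 cm. Otherwise 1 − V/(4πr³/3), with overlap V = π(R+r−d)²(d²+2dr−3r²+2dR+6rR−3R²)/(12d).

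**Example, r = 4, R = 5.**
- d = 1.0: PTV loss = 0.150 − 0.0005 = 15.0%; CTV loss = 0.
- d = 1.3: PTV loss = 0.195 − 0.0011 = 19.4%. V = π(7.7)²(22.09)/15.6 = 263.7 cc against 268.1 cc, so CTV loss = 1.6%.

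**Results (points of V95%, PTV loss / CTV loss).** The last column averages over d ~ Normal(1.3, 0.5).

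| r (cm) | d = 1.0 | d = 1.3 | d = 2.95 | averaged |
|---|---|---|---|---|
| 3 | 18.7 / 0 | 24.2 / 2.3 | 52.8 / 39.5 | 24.2 / 5.1 (ratio 4.7) |
| 4 | 15.0 / 0 | 19.4 / 1.6 | 43.0 / 28.8 | 19.4 / 3.7 (ratio 5.3) |
| 5 | 12.5 / 0 | 16.2 / 1.2 | 36.1 / 22.5 | 16.2 / 2.8 (ratio 5.8) |
| 5.67 | 11.2 / 0 | 14.6 / 1.1 | 32.6 / 19.5 | 14.6 / 2.4 (ratio 6.0) |

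Across volumes of 100 to 763 cc, ellipsoids, and gamma or Maxwell shift distributions, the averaged ratio stays at about 4.3 to 6.0. At a fixed 1.3 cm it is about 10 to 14. At 2.95 cm it is 1.3 to 1.7. At 1 cm or less CTV loss is zero and the ratio is not finite. If ±0.5 cm is the spread of daily shifts, the share at or below 1 cm is Φ((1.0 − 1.3)/0.5) = Φ(−0.6) = 27%.

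**Check of the model against section 2.2.3.** The measured volume outside 5 mm is 29.5/763 = 3.9%. The same model with a 5 mm margin predicts 54 cc at a fixed 1.3 cm and about 58 cc averaged, roughly double. The model is crude; this does not show an error in the documents. Scaling the shifts by 0.74 (mean 0.96 cm) to match 29.5 cc gives, at a 1 cm margin, PTV loss 10.8 and CTV loss 0.6, a ratio of about 19. PTV loss exceeds CTV loss in every case tried.

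**The case against.** PTV V95% is the protocol's own coverage criterion, so change in it is a coherent plan-quality measure. That stands, and it is a reason to keep it.

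The size is open to challenge. The motion data are whole-stomach data from five lymphoma patients, and section 2.2.3 does not say whether ±0.5 cm is between patients or between fractions. In this trial CTV_primary is the GTV plus expansions. Patients are aligned to CTV_elective, which ideally should not change, so part of the PTV may not move with the stomach. Full coverage at planning does not mean that the isodose stops at the PTV edge: if it lay 5 mm beyond, averaged PTV loss for radii of 3 to 5 cm would fall from 16–24 points to 7–11. All of this stands against any single figure. A reader might infer that the trial will report under-dosing about five times too large; the documents give no such number, and the ratio varies too widely with the assumptions to support one.

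A reader might also infer that the tumor would have been fully treated without adaptation on days with shifts under 1 cm. The overlay is a snapshot and leaves out motion during delivery; section 6.2.5 sets a 5 mm gating boundary. Adding 5 mm in the same direction, as an assumed worst case, gives CTV loss of 3.0 to 5.5 points at a 1.0 cm shift and brings the averaged ratio down to about 2. Snapshot CTV coverage can therefore understate under-dosing, so it belongs beside PTV coverage and should not displace it.

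**Conclusion.** The point holds as a mismatch between objective, measure and interpretation. Under the overlay in section 6.2.6, read as applying to the PTV grown on each day's CTV, PTV coverage falls before CTV coverage does, and reading it as tumor dose overstates under-dosing. Confidence is high for that direction. The ratio of about 4 to 6 is conditional on a spherical or ellipsoidal target, rigid shifts, an isodose at the PTV edge, and 1.3 ± 0.5 cm taken as the distribution of shifts; it should be quoted only with those conditions and the wider range shown above.

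It would be tempting to say that the case for adaptive treatment rests on this number. The documents do not support that. Section 3.0 lists the endpoint as exploratory, section 14 attaches no hypothesis or decision rule to it, and the comparison with historical controls in section 2.3.2 has no rule either. The pCR analysis is untouched. The correction is still worth making, because the justification as written directs the reader to the wrong conclusion.

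**What to change.** - In sections 3.0 and 6.2.6, add V95% and D95 of the daily GTV and CTV_primary under the overlaid initial plan as the measures of tumor dose. Report the same quantities separately under each day's adapted plan, so that the no-adaptation comparison and the adapted treatment are not confused.
- Keep PTV V95% beside them, labelled as plan quality or loss of margin.
- Rewrite the justification in section 3.0 so that PTV coverage is not read as a percent of prescription delivered to the tumor, and so that the overlay is described as the un-adapted plan.
- State in section 6.2.6 which CTVs the analysed PTV includes, and that the snapshot overlay does not capture motion during delivery.

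The cost is a few more dose-volume readouts. The daily contours are already drawn, and contours and plans already go to central review. No patient procedure, treatment or sample size changes.

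### Section 3.0 reads the exploratory dosimetry endpoints as dose delivered, but the only method described recalculates the initial plan, which differs from the delivered plan on every adapted fraction

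*Combined protocol and SAP*

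**What the plan says.** The exploratory objective in Section 3.0 is "To quantify the deviation in dose to the tumor due to variation in stomach position", and its endpoint is "Average percent difference in coverage of PTV by 95% isodose line". The justification column says that the mean over the five treatments "represents approximately what percent of the total planned prescription was delivered to the target" and adds that under-dosing from organ motion may reduce tumor control. The OAR endpoint has a parallel justification: it is read as the share of the prescription that reached the OAR, with over-dosing tied to possible toxicity. Section 3.0 does not name the plan from which either difference is computed.

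Section 6.2.6 gives the only method: "Initial radiation treatment plans will be overlaid on each daily anatomy and the change in dose to PTV and OARs will be determined".

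On what patients receive, Section 6.2.1 says "Radiation must be delivered with daily adaptive planning and MR gating or CBCT breath hold treatment", then "The stomach and OARs must be redrawn each day for the adaptive plan", then "Plans should be adapted to meet OAR constraints or improve coverage as needed for each day's unique anatomy". Its coverage goal is PTV V95% = 100%. The Protocol Summary also treats recalculating the initial plan on the day's images as a step separate from the treatment then given.

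Section 14 specifies no analysis for the dosimetric endpoints.

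**The concern.** An initial plan recalculated on the day's anatomy answers a useful question: how far would dose have moved if nothing had been adapted? It does not say what dose was given on a day when the plan was changed. If the overlay results are published under the interpretation in Section 3.0, a coverage deficit that adaptation was meant to remove could be described as under-dosing of the tumor. A bowel dose that adaptation was meant to bring down could likewise be described as over-dosing. If someone then related those values to local control or grade 3 or higher toxicity, the exposure would be wrong for every adapted fraction.

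The trial could also miss a result within its reach. Reducing the effect of stomach motion is central to the rationale in Section 2.1. Setting the delivered plan against the non-adapted plan in the same patient would show what adaptation achieved, and the documents do not specify that contrast.

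**Working it through.** The plan states no expected value, power or interval for these endpoints, so there is no figure to reproduce. The check is on definitions.

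**1. What the overlay measures.** For patient *i* and fraction *j*, let
- C = PTV coverage (V95%) of the initial plan on the simulation anatomy;
- N(ij) = V95% of that same plan on the anatomy of day *j*, which is the overlay in Section 6.2.6;
- D(ij) = V95% of the plan delivered on day *j*, under Section 6.2.1.

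Overlay endpoint: mean over *j* of 100 × (N(ij) − C) / C.

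Delivered-plan endpoint: mean over *j* of 100 × (D(ij) − C) / C.

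Delivered minus overlay: mean over *j* of 100 × (D(ij) − N(ij)) / C.

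A fraction contributes zero to the last line if the initial plan was used unchanged, because then D = N. Otherwise it contributes the change in coverage due to adaptation. If C = 100%, a share *a* of a patient's fractions is adapted, and adaptation changes V95% by a mean of *g* points on those fractions, the error in reading the overlay as delivered is *a* × *g* points. With five fractions, *a* can be 0, 0.2, 0.4, 0.6, 0.8 or 1. The documents give neither *a* nor *g*. The error is zero only if *a* = 0 or *g* = 0. The same algebra holds for OAR dose.

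**2. Whether V95% can be read as percent of prescription.** Take the 95% isodose relative to the 25 Gy prescription (an assumption, since Section 6.2.1 does not spell it out). The threshold is 0.95 × 25 = 23.75 Gy. Two hypothetical uniform doses show the problem:
- the whole PTV at 96% of prescription, 0.96 × 25 = 24.0 Gy: V95% = 100%;
- the whole PTV at 94% of prescription, 0.94 × 25 = 23.5 Gy: V95% = 0%.

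A 0.5 Gy change in dose moves the coverage measure across its full range. V95% says how much volume passes a threshold. It does not say what share of the prescription arrived. A percent difference is also a change, so no deviation gives 0, which cannot mean that 0% was delivered. The interpretation would therefore fail even for a delivered plan.

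**3. Whether another comparator rescues it.** The change in dose in Section 6.2.6 could mean overlay against initial plan, or overlay against adapted plan. The first is the effect of motion without adaptation. The second is the effect of adaptation. Neither is the percent of prescription delivered.

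**4. Whether the preliminary data give a size.** Section 2.2.3 reports 29.5 cc of an average 763 cc stomach outside the margin: 29.5 / 763 = 3.9%. That figure is stomach volume in patients with gastric lymphoma at a 5 mm PTV margin. The endpoint here is PTV coverage by an isodose, with a 1 cm PTV margin around an already expanded CTV (Section 6.2.4). The 3.9% does not measure this endpoint and cannot stand in for *g*.

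**The case against.** The strongest reply is that objective, endpoint and method agree. The objective is deviation due to stomach position, and an overlay on daily anatomy measures that. What is wrong is then one hedged sentence in a justification column, repeated for OARs, and a report labelled as Section 6.2.6 describes would mislead nobody. Much of this stands. The overlay is valid for its objective and should be kept. The link from Section 3.0 to Section 6.2.6 is also an inference, though a fair one, since no other method is given. But Section 3.0 is where the plan says what the number means, and that meaning is wrong for adapted fractions.

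A reader might infer more than the documents support:
- **That no patient received the dose in the overlay, or that the trial is bound to report false under-dosing.** Plans are adapted as needed, so on some fractions the initial plan may be the delivered plan. How the results will be labelled is not yet known.
- **That a dose-outcome analysis is compromised.** None is specified. The remarks on tumor control and toxicity are rationale, worded as possibilities.
- **That no within-patient comparison is planned, because Section 2.3.2 says "We will compare the dosimetric and clinical outcomes to historical controls".** That sentence is general and not tied to this endpoint, and the endpoint is itself a within-patient difference. What is missing is an explicit contrast of delivered with non-adapted plans.
- **That the shortfall would be about 3.9%.** See step 4 of the working.

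**Conclusion.** The point holds as an error of interpretation in the exploratory endpoints. Section 3.0 describes as delivered a quantity that, by the only method given, equals the delivered plan's value only where the initial plan was used unchanged. On adapted fractions it is a counterfactual, and it could be reported as under- or over-dosing that did not occur. Separately, V95% is a volume measure and cannot be read as percent of prescription under any choice of plan.

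The size is unknown: *a* × *g* for each patient, with neither term in the documents. The conclusion assumes that Section 6.2.6 is how the Section 3.0 endpoints will be computed. The primary pCR analysis, the 36-patient sample size and the secondary endpoints are unaffected, so this is a low-severity point that is worth fixing because it is cheap.

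**What to change.** 1. In Section 3.0, name the overlay results as predicted non-adapted PTV coverage and predicted non-adapted OAR dose, and delete the reading as percent of prescription delivered in both justification cells.
2. In Section 6.2.6, state the comparator and add the same quantities computed from the plan delivered at each fraction.
3. In Section 14, add a short paragraph: for each patient, average delivered minus non-adapted over the fractions received, then report the mean of these patient-level values with a 95% confidence interval. The patient is the unit, so fractions are not counted as independent observations. Also report the share of fractions adapted.
4. State that any remark on tumor control or toxicity will use delivered-plan dose only.

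The cost is a few sentences and some extra extraction from planning datasets already sent for central review. The sponsor should first confirm that those transfers include each fraction's adapted plan, and not only the initial plan and the daily images.
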